3.2 Exclusion Criteria

Participants who exhibit any of the following conditions at screening will not be eligible for admission into the study.

3.2.1 Participants who have had chemotherapy or radiotherapy within 3 weeks prior to entering the study or those who have not recovered from clinically significant adverse events due to agents administered more than 3 weeks earlier. The Principal Investigator or treating investigator determine if any abnormal laboratory values or toxicities are due to prior agents administered vs. disease and if they are clinically significant.

3.2.2 Participants may not be receiving any other study agents.

3.2.3 Known CNS involvement with CLL or T-LGL.

3.2.4 History of allergic reactions or sensitivity to pyrimethamine.

3.2.5 Patients taking folic acid are eligible if the folic acid is discontinued prior to pyrimethamine administration and not taken for the duration of time enrolled on this study.

- 3.2.6** Prior allogeneic SCT is an exclusion only if the subject has active graft vs host disease or requires immunosuppression other than a constant stable dose of glucocorticoids (the latter is permitted).
- 3.2.7** Uncontrolled intercurrent illness including, but not limited to, ongoing or active infection not controlled by appropriate antibacterial, antiviral or antifungal therapy, symptomatic congestive heart failure, unstable angina pectoris, clinically significant cardiac arrhythmia, or psychiatric illness/social situations that would limit compliance with study requirements.
- 3.2.8** Pregnant women are excluded from this study because pyrimethamine is a/an class C agent with the potential for teratogenic or abortifacient effects. Because there is an unknown but potential risk of adverse events in nursing infants secondary to treatment of the mother with pyrimethamine, breastfeeding should be discontinued if the mother is treated with pyrimethamine. These potential risks may also apply to other agents used in this study.
- 3.2.9** HIV-positive individuals on combination antiretroviral therapy are ineligible because of the potential for pharmacokinetic interactions with pyrimethamine. In addition, these individuals are at increased risk of lethal infections when treated with marrow-suppressive therapy. Appropriate studies will be undertaken in participants receiving combination antiretroviral therapy when indicated.

3.3 Inclusion of Women, Minorities and Other Underrepresented Populations

The investigators will work hard to enroll women and minorities on this clinical trial. CLL is approximately two-fold more common in men than women but we will aim for representation of women at least equivalent to the balance among those diagnosed with the disease. The Inclusion / Exclusion criteria are broad and should not have a negative impact on accrual of underrepresented populations.

4. REGISTRATION PROCEDURES

4.1 General Guidelines for DF/HCC and DF/PCC Institutions

Institutions will register eligible participants with the DF/HCC Quality Assurance Office for Clinical Trials (QACT) central registration system. Registration must occur prior to the initiation of therapy. Any participant not registered to the protocol before treatment begins will be considered ineligible and registration will be denied.

A member of the study team will confirm eligibility criteria and complete the protocol-specific eligibility checklist.

Following registration, participants may begin protocol treatment within two weeks. Issues that would cause treatment delays should be discussed with the Principal Investigator. Minor delays due to physician clinic schedule, holidays, vacations, etc. are permitted. If a participant does not receive protocol therapy following registration as described herein, the participant's protocol status should be changed. Notify the QACT Registrar of participant status changes as soon as possible.

4.2 Registration Process for DF/HCC and DF/PCC Institutions

The QACT registration staff is accessible on Monday through Friday, from 8:00 AM to 5:00 PM Eastern Standard Time. In emergency situations when a participant must begin treatment during off-hours or holidays, call the QACT registration line at [contact] and follow the instructions for registering participants after hours.

The registration procedures are as follows:

1. Obtain written informed consent from the participant prior to the performance of any study related procedures or assessments.
2. Complete the protocol-specific eligibility checklist using the eligibility assessment documented in the participant's medical/research record. **To be eligible for registration to the study, the participant must meet each inclusion and exclusion criteria listed on the eligibility checklist unless granted an eligibility deviation from the Regulatory Sponsor and the IRB.**

Reminder: Confirm eligibility for ancillary studies at the same time as eligibility for the treatment study. Registration to both treatment and ancillary studies will not be completed if eligibility requirements are not met for all studies.

3. Fax the eligibility checklist(s) and all pages of the consent form(s) to the QACT at [contact].

Exception: DF/PCC Affiliate sites must fax the entire signed consent form including HIPAA Privacy Authorization and the eligibility checklist to the Network Affiliate Office. The Network Affiliate Office will register the participant with the QACT.

4. The QACT Registrar will (a) validate eligibility, (b) register the participant on the study, and (c) randomize the participant when applicable.
5. The QACT Registrar will send an email confirmation of the registration and/or randomization to the person initiating the registration immediately following the registration and/or randomization.

5. TREATMENT PLAN

Treatment will be administered on an outpatient basis. Expected toxicities and potential risks as well as dose modifications for pyrimethamine are described in Section 6 (Expected Toxicities and Dosing Delays/Dose Modifications). No investigational or commercial agents or therapies other than those described below may be administered with the intent to treat the participant's malignancy.

Subjects will self-administer this oral drug once daily, in the morning, with food. Dose is to be held until lab work results are reported on days that subjects are scheduled for clinic (i.e, Cycle 1 Day 1, 8 and 15, Cycle 2 Day 1, etc.). Therapy will be continuous, with one cycle arbitrarily defined as 28 days (+/- 3 days). All subjects will initially be treated for one 28 day cycle, followed by response and toxicity evaluation. On the day of a clinic visit, subjects will delay taking their dose until after their laboratory tests have been drawn at clinic. The subject may delay eating or eat again after the dose. This will be noted on the diary.

At screening all subjects will be assessed by blood draw for folate deficiency prior to initiating study therapy. Those found to be deficient will be repleted with folic acid, 1 mg. per day for at least 7 days, until level reaches normal range. If deficient at baseline, folate level should be redrawn approximately every month while on study drug, or at required visits, whichever is less. Once within normal range, subjects should discontinue supplemental folate administration. Baseline assessments will not need to be repeated if they fall out of screening window due to folate repletion.

The initial component of this study will be a Phase I dose escalation to assess the safety of pyrimethamine in this patient population. The first three dose levels below were completed with expansion, but the PK and PD data suggested inadequate blood drug levels. For that reason and because the safety data thus far look good (see below), cohorts 4 and 5 have been added as per the table.

Table 1: Dose-Escalation Schedule

Dose-Escalation Schedule 1 cycle = 28 days (+/- 3 days)		
	Dose Level	Dose of Pyrimethamine
Starting Dose →	1	12.5 mg, Once Daily*
	2	25 mg, Once Daily
	3	50 mg, Once Daily
	4	100 mg Once Daily
	5	150 mg Once Daily

Following completion of the additional cohorts of the Phase 1 study, the PK, PD and safety data will be assessed to determine the recommended Phase 2 dose. Any subjects who are continuing on study from the Phase I portion, who are deriving clinical benefit without significant toxicity and who are currently on a lower dose than the recommended Phase 2 dose, may be considered for dose escalation to the newly determined Phase 2 dose, at the discretion of the treating physician and the Principal Investigator.

*The 25 mg tablet is scored, and will be split in half either by the research nurse or pharmacist.

5.1 Pre-treatment Criteria

5.1.1 Cycle 1, Day 1

There should be no clinically significant change in the status of the patient between screening and C1D1. If there is, the laboratory values of the eligibility criteria should be rerun, and the patient approved for study start by the treating physicians or PI. As per Section 9, Study Calendar, CBCD and chemistries should be drawn on Day 1 of each cycle.

5.1.2 Subsequent Cycles

All toxicities for which pyrimethamine was held must have resolved to grade 1 or less prior to re-initiation of study therapy. For a detailed discussion of the management of hematologic toxicity **please see section 6.3.1**

5.2 Agent Administration

5.2.1 Pyrimethamine

- Administration – Subjects will self-administer Pyrimethamine once daily, in the morning, with food.
- Dosing – The daily dose will be determined during the Phase I study by the cohort to which the study is enrolling. (See Table 1: Dose-Escalation Table, Section 5.0) Following the determination of the Phase 2 dose, all subjects will be enrolled to that dose level.
- Hydration – No hydration is required. *
- Oral Doses – The daily dose should be administered with food. Any doses vomited within one hour of administration should be retaken. Any doses missed can be taken later on the same day they were missed, with food. If a missed dose is not discovered until the following day, the dose should not be made up. There are no foods or liquids that are contraindicated.

*Investigators should monitor patients for tumor lysis with labs twice per week in the first cycle and at least weekly thereafter (in the first cycle), and subjects will be encouraged to maintain oral hydration. Intravenous hydration or additional treatment for TLS should commence if any laboratory evidence of such is demonstrated. At a minimum, hyperuricemia, hydration, and electrolyte disturbances will be monitored closely and addressed promptly.

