6.1.1 Adverse Event Lists(s) for Pyrimethamine

Hypersensitivity reactions, occasionally severe (such as Stevens-Johnson syndrome, toxic epidermal necrolysis, erythema multiforme, and anaphylaxis), and hyperphenylalaninemia, can occur particularly when **pyrimethamine** is administered concomitantly with a sulfonamide. Anorexia and vomiting may occur. Vomiting may be minimized by giving the medication with meals; it usually disappears promptly upon reduction of dosage. Higher doses may produce megaloblastic anemia, leukopenia, thrombocytopenia, pancytopenia, atrophic glossitis, hematuria, and disorders of cardiac rhythm. Hematologic effects, however, may also occur at low doses in certain individuals. Pulmonary eosinophilia has been reported rarely.

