6.2 Toxicity Management

Following the ingestion of 300 mg or more of **pyrimethamine**, gastrointestinal and/or central nervous system signs may be present, including convulsions. The initial symptoms are usually gastrointestinal and may include abdominal pain, nausea, severe and repeated vomiting, possibly including hematemesis. Central nervous system toxicity may be manifest by initial excitability, generalized and prolonged convulsions which may be followed by respiratory depression, circulatory collapse, and death within a few hours. Neurological symptoms appear rapidly (30 minutes to 2 hours after drug ingestion), suggesting that in gross overdose pyrimethamine has a direct toxic effect on the central nervous system. The fatal dose is variable, with the smallest reported fatal single dose being 375 mg. There are, however, reports of pediatric patients who have recovered after taking 375 to 625 mg.

There is no specific antidote to acute pyrimethamine poisoning. In the event of overdose, symptomatic and supportive measures should be employed. Gastric lavage is recommended and is effective if carried out very soon after drug ingestion. Parenteral diazepam may be used to control convulsions. Folinic acid should also be administered within 2 hours of drug ingestion to be most effective in counteracting the effects on the hematopoietic system. Due to the long half-life of pyrimethamine, daily monitoring of peripheral blood counts is recommended for up to several weeks after the overdose until normal hematologic values are restored.

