6.3.2 Rash

For grade 3 or greater skin rash, study drug should be discontinued. If the rash resolves (back to grade 1 or less, within 4 weeks) with supportive care and is not IgE mediated or accompanied by other signs of allergic hypersensitivity, patients may resume study therapy at one lower dose level, or if already at the lowest dose level, may resume at that dose with addition of prophylactic antihistamine. Consideration may be given to use of a prophylactic antihistamine, particularly diphenhydramine, even in patients resuming at a reduced dose.

6.3.3 Anorexia/Vomiting:

For grades 1-4 anorexia/vomiting, study drug should be continued with initiation of antiemetic therapy. If drug needs to be held until patient can tolerate drug with supportive care, patient may resume at same dose level. If antiemetics do not bring relief, then the dose should be reduced one level. Patients with grade 3 or 4 anorexia/vomiting that do not respond to supportive care should be discontinued from study drug, but will remain on study for follow-up procedures until initiation of another therapy.

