7. DRUG FORMULATION AND ADMINISTRATION

7.1 Pyrimethamine

7.1.1 Description

The chemical name of pyrimethamine is 5-(4-chlorophenyl)- 6-ethyl-2,4-pyrimidinediamine. It acts as a folate antagonist and a STAT3 inhibitor.

Pyrimethamine is well absorbed orally with peak levels occurring between 2 to 6 hours following administration. It is eliminated slowly and has a plasma half-life of approximately 96 hours. Pyrimethamine is 87% bound to human plasma proteins.

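### The rule to retake a dose vomited within one hour has no cap, so at the added 150 mg level one retake brings the amount swallowed to 300 mg, where Section 6.2 warns of convulsions

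*Combined protocol and SAP*

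**What the plan says.** Section 5.2.1 (Oral Doses) gives the rule without qualification: "Any doses vomited within one hour of administration should be retaken". The special instructions in the Appendix C diary use the same words. The nursing education sheet states it in reverse: a vomited dose is made up only if the vomiting came within an hour. None of them sets a maximum number of retakes, distinguishes dose levels, or asks the participant to call first.

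Section 5 explains that "cohorts 4 and 5 have been added as per the table". Table 1 there lists level 4 as 100 mg and level 5 as 150 mg once daily, above the 50 mg of level 3.

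Section 6.2 describes overdose. From 300 mg ingested, "gastrointestinal and/or central nervous system signs may be present, including convulsions". It adds: "The initial symptoms are usually gastrointestinal and may include abdominal pain, nausea, severe and repeated vomiting". It gives lethality as variable, "with the smallest reported fatal single dose being 375 mg", and says that there is no specific antidote. It puts the onset of neurological symptoms at 30 minutes to 2 hours.

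Section 6.1.1 lists vomiting as an expected effect and says that "it usually disappears promptly upon reduction of dosage". Section 6.3.3 opens its vomiting guidance with "For grades 1-4 anorexia/vomiting, study drug should be continued with initiation of antiemetic therapy".

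**The concern.** The retake rule gives little cause for worry when the top dose is 50 mg. At 150 mg the assigned dose is half of the Section 6.2 figure, so a single retake uses up the whole margin in amount swallowed. The symptom that triggers the retake is also one that Section 6.2 lists among the first signs of too much drug. The one-hour retake window overlaps the 30-minute to 2-hour window for neurological onset, so a participant could redose before CNS signs appear.

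On most days the participant is at home with a written instruction to retake, and nothing in it says when to stop. What is at stake is participant safety at the two added levels. If 150 mg becomes the Phase 2 dose, the rule would reach the 20 additional Phase II patients (Section 14.1.2), and continuing Phase I participants could be escalated to that dose (Section 5).

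**Working it through.** The documents give no figure for this point, so there is none to reproduce.

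**1. Amount swallowed.** Inputs: the dose levels in Table 1 of Section 5 and the 300 mg and 375 mg figures in Section 6.2. Amount swallowed = dose × (1 + number of retakes).

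| Level | Dose (mg) | 1 retake (mg) | 2 retakes (mg) | Retakes to reach 300 mg |
|---|---|---|---|---|
| 1 | 12.5 | 25 | 37.5 | 23 |
| 2 | 25 | 50 | 75 | 11 |
| 3 | 50 | 100 | 150 | 5 |
| 4 | 100 | 200 | 300 | 2 |
| 5 | 150 | 300 | 450 | 1 |

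**2. Amount absorbed at level 5 after one retake.** The documents do not say how much of a vomited dose is kept, so this step rests on assumptions: one compartment, first-order absorption with no lag, and complete absorption of whatever is not vomited. Section 7.1.1 supplies the half-life of about 96 h and "peak levels occurring between 2 to 6 hours following administration".

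- Elimination rate: ke = ln 2 / 96 = 0.00722 per hour.
- The absorption rate ka solves ln(ka/ke) / (ka − ke) = tmax. This gives ka = 3.03 per hour for tmax 2 h and 0.790 per hour for tmax 6 h.
- Fraction absorbed before vomiting at time t = 1 − exp(−ka × t).
- Total absorbed = 150 × (1 + fraction).

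| Time of vomiting | Fraction (tmax 6 h to 2 h) | Total absorbed (mg) |
|---|---|---|
| Before any absorption | 0 | 150 |
| 30 minutes | 0.33 to 0.78 | 199 to 267 |
| 60 minutes | 0.55 to 0.95 | 232 to 293 |

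So 300 mg swallowed corresponds to 150 to about 293 mg absorbed.

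**3. Cost of not retaking a dose.** Daily retention is r = 0.5^(24/96) = 0.841. Ignoring the short absorption phase, skipping dose n lowers the next trough by the fraction (1 − r) / (1 − r^n).

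- Dose 1: 0.159 / 0.159 = 100%.
- Dose 3: 0.159 / (1 − 0.595) = 39%.
- Dose 7: 0.159 / (1 − 0.297) = 23%.
- Steady state: 1 − 0.841 = 15.9%.

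**4. Effect of a cap.** With no retake at 150 mg and at most one per day at 100 mg and below, the largest amount swallowed in a day is 150 mg at level 5, 200 mg at level 4 and 100 mg at level 3. All are below 300 mg.

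**The case against.** The strongest reply is that retakes apply only to doses that came back up, so the amount swallowed overstates exposure. That stands: the absorbed total in step 2 never reaches 300 mg. Its upper end needs rapid absorption, no lag despite dosing with food, and vomiting right at the hour. Against that, Section 6.2 states its warning by amount ingested, and nothing bars a second retake.

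The second reply is that the protocol already manages vomiting. That also largely stands. Beyond its opening sentence, Section 6.3.3 allows holding drug, requires a one-level reduction if antiemetics fail, and stops drug for grade 3 or 4 vomiting that does not respond to supportive care. Under Section 5.3, grade 4 vomiting in cycle 1, or grade 3 despite optimal prophylaxis, is a DLT, and Section 6.3 then holds therapy. A reader might infer from the opening sentence that severe vomiting goes unmanaged, and these provisions show otherwise. But they are clinicians' decisions, made after the event is reported. None limits same-day retakes by a participant following the diary.

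Third, supervision is better than it first appears. On clinic days the dose waits for laboratory results, and the two-hour post-dose sample on Cycle 1 Day 1 (Section 8.2) carries the first dose past the retake window. Level 5 opens only after 100 mg has cleared the 3+3 rules. This narrows the exposure to days at home but does not remove it.

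Fourth, accumulation dwarfs a retake. At 150 mg daily the same model gives a steady-state body load of 150 / (1 − 0.841), about 943 mg, and one retake adds at most 150 × 0.95, about 143 mg, or 15%. That limits any claim about chronic exposure. The Section 6.2 warning concerns acute ingestion, which is a separate matter.

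**Conclusion.** The gap is real and specific. An uncapped retake rule, carried into the added levels, reaches the protocol's own 300 mg ingestion figure after one retake at 150 mg and after two at 100 mg. No other section limits same-day retakes. The amounts swallowed are plain arithmetic. The absorbed range of 150 to about 293 mg depends on the absorption assumptions above. The documents give no frequency of vomiting at 150 mg, so the number of participants affected cannot be estimated.

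Two stronger readings should be resisted. A reader might infer that the rule leads to a potentially fatal dose. The 450 mg figure needs two successive vomits, each within the hour, and it is a total of partly lost doses, whereas 375 mg is a fatal single dose. Section 6.2 also reports pediatric recoveries after 375 to 625 mg. A reader might also infer that retakes bias the MTD by crediting a DLT to 150 mg when more was absorbed. The documents give no basis for a size, and at steady state the added load is about the same as the roughly 16% effect of losing a dose, so it is hard to call one large and the other small.

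This is a cheap safety improvement. It touches no endpoint, sample size or error rate.

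**What to change.** In Section 5.2.1, the Appendix C diary and the nursing education sheet, state that:

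- a participant taking 150 mg daily does not retake a vomited dose and takes the next one the following day;
- a participant taking 100 mg or less may retake once per day at most;
- a participant taking 100 or 150 mg calls the site before the next dose after repeated vomiting.

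Tie the rule to the dose currently being taken, so that it still applies after a reduction under Table 2 of Section 6.3. A ban at 100 mg is not needed, because one retake there gives 200 mg swallowed. Section 6.3.3 does not need a further hold rule for this purpose.

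The cost is wording in three places and an occasional lost dose at level 5. That loss lowers the next trough by about 16% at steady state, about 39% if it is dose 3, and entirely if it is dose 1. The early losses deserve acknowledgement, because levels 4 and 5 were added when blood levels looked inadequate, but each affects a single dose.

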# pills/caps/tabs that should have been taken:	
Discrepancy Notes:	

SPECIAL INSTRUCTIONS:

- * Please remember to take Allopurinol as prescribed, 300 mg once per day, on days 1 through 10
- * Please keep track of the Allopurinol on this diary, as in example to the left.
- * Drug must be kept in original container.
- * There are no restricted foods or beverages
- * Any doses missed can be taken later on the same day they were missed, with food.
- * If a missed dose is not discovered until the following day, the dose should not be made up.
- * Any doses vomited within one hour of administration should be retaken
- * Please remember to bring any unused study drug, all empty containers, and diary to the next clinic visit.

**Dana-Farber Cancer Institute
Nursing Protocol Education Sheet**

Protocol Number:	09-421
Protocol Name:	A phase I/II study of Pyrimethamine, a STAT3 inhibitor, for the treatment of relapsed Chronic Lymphocytic Leukemia/Small Lymphocytic Lymphoma and T-LGL
DFCI Site PI:	[name], PhD
DFCI ResearchNurses:	[name]; [name]; [name]

Page the DFCI research nurse or DFCI site PI if there are any questions/concerns about the protocol.
Please also refer to **ONC 15: Oncology Nursing Protocol Education Policy**

SPECIAL NURSING CONSIDERATIONS UNIQUE TO THIS PROTOCOL

Study Design	Pyrimethamine is an oral folic acid antagonist used as an antiparasitic agent. See section 2.1 for description of this agent, precautions in people with possible folate deficiency and for potential toxicities, like myelosuppression, vomiting, anorexia, etc... Current dose as per A.P. Each cycle = 28 days.
Dose Calculation	Doses of Pyrimethamine are fixed in mg The Recommended Phase II dose is found as noted on Alert Page
Study Drug and Administration	Pyrimethamine- See TREATMENT PLAN – sec. 5 
 • Self-administered, once daily in the AM with food. • Instruct patient to not take drug at home on clinic visit days (e.g. Cycle 1 Day 1,8, and 15, C2D1, etc...). Dose is not to be taken until labs results are reviewed on those days. • Instruct patients on Drug Diary use. • Vomited doses not made up unless vomited within 1 hr of intake. Missed, e.g. forgotten doses can be made up on same day but not later • Section 5.1 Pre treatment criteria • Section 5.2 Agent Administration, to include twice weekly labs in Cycle 1 for TLS monitoring.

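### The retake rule for vomited doses has no cap and no exception at the added 100 and 150 mg levels; at 150 mg one retake means 300 mg swallowed, the amount Section 6.2 links to possible convulsions

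*Combined protocol and SAP*

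**What the plan says.** Pyrimethamine is self-administered once daily. Section 5.2.1 states that "Any doses vomited within one hour of administration should be retaken". The Appendix C diary, which the patient holds, carries the same instruction. The Nursing Protocol Education Sheet puts it from the other side: "Vomited doses not made up unless vomited within 1 hr of intake". In none of the three places is there a maximum number of retakes, a daily ceiling, an exception by dose level, or a request to call the site first.

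Table 1 in Section 5 now runs to 100 mg (level 4) and "150 mg Once Daily" (level 5). Both levels were added after the first three, which ended at 50 mg.

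Section 6.2 describes acute toxicity. "Following the ingestion of 300 mg or more of" pyrimethamine, it says, "gastrointestinal and/or central nervous system signs may be present, including convulsions". It adds that "Neurological symptoms appear rapidly (30 minutes to 2 hours after drug ingestion"), attributes a direct central nervous system effect to gross overdose, and gives 375 mg as the lowest single dose reported as fatal.

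Section 6.3.3 handles anorexia and vomiting through antiemetics, holding the drug and reducing the dose. It does not mention retaking a dose on the same day.

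**The concern.** The rule gives ample room at 50 mg, where one retake brings the swallowed amount to 100 mg. Tripling the top dose removes that room. Other dosing text still fits a 50 mg ceiling: Section 7.1.2 lists at most two 25 mg tablets a day, while 150 mg needs six, and Section 2.1 still calls 50 mg the trial's maximum. This suggests that the retake rule was carried over without being reconsidered, although the documents do not say so.

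What is at stake is patient safety. Vomiting is an expected effect of the drug, and Section 6.2 lists repeated vomiting among the early signs of overdose. An uncapped instruction can therefore lead a patient whose vomiting is already a sign of toxicity to take more drug. On days without a clinic visit this can happen before the site knows of it. Section 6.2's onset time for neurological symptoms, 30 minutes to 2 hours, overlaps the period in which a prompt retake would be taken. A retake of unknown time and amount would also make a Cycle 1 event at level 5 harder to interpret as a dose-limiting toxicity.

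**Working it through.** The plan gives no figure of its own for this point, so there is none to reproduce.

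**Inputs.** Dose levels: Table 1, Section 5. Amounts of 300 mg and 375 mg: Section 6.2. Half-life of about 96 hours and peak level at 2 to 6 hours: Section 7.1.1. Cycle of 28 daily doses: Section 5. The fraction f of the first dose lost by vomiting is not given, so the whole range from 0 to 1 is shown.

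**Step 1: amount swallowed** = dose × (1 + number of retakes).

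| Dose level | One retake | Two retakes | Retakes needed to reach 300 mg |
|---|---|---|---|
| 50 mg | 100 mg | 150 mg | 5 |
| 100 mg | 200 mg | 300 mg | 2 |
| 150 mg | 300 mg | 450 mg | 1 |

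Of the five levels, only 150 mg reaches 300 mg with a single retake. Two retakes there also pass 375 mg.

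**Step 2: amount retained at 150 mg after one retake**, if the second dose is kept = 150 × (1 − f) + 150.

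| f | 0 | 0.25 | 0.5 | 0.75 | 1 |
|---|---|---|---|---|---|
| Retained (mg) | 300 | 262.5 | 225 | 187.5 | 150 |

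Since levels peak only 2 to 6 hours after a dose, much of a dose vomited within one hour may be lost. The low end of the retained range is therefore plausible.

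**Step 3: retake compared with ordinary 150 mg dosing.** Assume one compartment, full absorption and a 96-hour half-life. The fraction left after a day is r = 2^(−24/96) = 0.841. The post-dose body load at dose n is 150 × (1 − r^n)/(1 − r), and the share contributed by the latest dose is w = (1 − r)/(1 − r^n). A retake raises the post-dose load by (1 − f) × w. Leaving a vomited dose unreplaced lowers the next trough by f × w.

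| Dose number | Ordinary load (mg) | w | Rise from retake, f = 0 | Rise from retake, f = 0.5 |
|---|---|---|---|---|
| 1 | 150 | 100% | 100% | 50% |
| 2 | 276 | 54% | 54% | 27% |
| 3 | 382 | 39% | 39% | 20% |
| 8 | 707 | 21% | 21% | 11% |
| Steady state | 943 | 16% | 16% | 8% |

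The column w is also the largest possible fall in the next trough if the dose is wholly lost (f = 1) and not replaced.

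**Step 4: cost of one unreplaced dose** = 1/28 = 3.6% of a cycle's planned dose.

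Sample size, power and type I error do not enter this point and are unaffected.

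**The case against.** The strongest reply is that vomited drug is not retained drug. The rule applies only to doses that came back up, so 300 mg retained requires that nothing was lost, which comes close to contradicting the trigger. Section 6.2 speaks of ingestion, sits in an overdose context and says only that signs may be present. This stands. A reader might infer that one retake at 150 mg delivers a convulsant dose, or that two deliver a fatal one; the documents do not show that partly vomited drug acts like the same amount kept down. What remains is that Section 6.2 states its warning by amount ingested, and that neither patient nor site can measure what was lost.

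A second reply is that ordinary dosing produces larger body loads. A Day 1 retake leaves at most 300 mg, less than the 382 mg load after the third ordinary dose, and at steady state the excess is at most 16%. This also stands for accumulated load, but load is not the same as an acute peak after a doubled intake.

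A third is that the largest relative increase, at dose 1, does not normally arise at home. On clinic days "Dose is to be held until lab work results are reported on days that subjects are scheduled for clinic", and Section 8.2 schedules a sample two hours after the Cycle 1 Day 1 dose. So the picture of an unobserved patient fits later doses, where the relative increase is at most 54% and falling.

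A fourth is that recurrent vomiting is managed under Section 6.3.3, with antiemetics and a dose reduction if they fail. That is correct; only the same-day retake is left open.

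A reader might also infer that the diary could not capture a retake. The available text of Appendix C may lack a daily dose log, so nothing can be concluded about what the diary records. Nor can the number of affected patients be estimated, because the documents give no rate of vomiting within one hour.

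**Conclusion.** The point holds as a gap in a safety instruction. The rule is uncapped and has no exception at the two added levels. At 150 mg one retake brings the amount swallowed to 300 mg, equal to Section 6.2's figure, with 150 to 300 mg retained. Two retakes bring it to 450 mg swallowed, above 375 mg. At 100 mg the 300 mg figure needs two retakes; at 12.5 to 50 mg no concern is shown.

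The conclusion rests on two readings. One is that a retake follows promptly: the rule times the vomiting and not the retake, but prompt retaking is the natural sense. The other is that Section 6.2's ingested amount is a fair warning level even when part of the dose is lost.

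The probability of harm cannot be stated. The case for a change is that of a low-cost precaution against a hazard of unknown size, which is enough to justify correcting the wording. The rule reaches beyond the level 5 cohort only if 150 mg is chosen as the Phase II dose; it would then cover up to 26 Phase II patients (6 carried over plus 20, Sections 14.1.2 and 14.2.2).

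A flat ban on home retakes might seem to follow, but it goes further than needed. Levels 4 and 5 were added because drug levels looked too low, and refusing every replacement early in Cycle 1 would lower exposure inside the only window for dose-limiting toxicity.

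**What to change.** Amend Section 5.2.1, the Appendix C diary and the nursing sheet with the same text:

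- At 150 mg, a vomited dose is not retaken unless the patient first calls the site and site staff approve it; at clinic, site staff decide. Never more than one retake.
- At 100 mg, at most one retake per day, which keeps the amount swallowed to 200 mg.
- Any retake is recorded with its time and amount, for review of dose-limiting toxicity.
- The rule for 12.5 to 50 mg stays as it is.

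A cap of one retake would not be enough at 150 mg, because it still allows 300 mg swallowed. The approval step lets staff judge how much was probably lost and whether the vomiting is itself a sign of toxicity.

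The cost is a wording amendment, a place to record the retake, some phone calls and an occasional unreplaced dose. Each such dose is 3.6% of a cycle's dose. It lowers the next trough by up to about 16% at steady state, and by more in the first days of Cycle 1: up to 54% for dose 2 and 100% for dose 1. That is why the decision is left to site staff and not barred. No extra patients, visits or procedures are needed.
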